2. ABBREVIATIONS

AE	Adverse Event
ADE	Adverse Device Effect
ASADE	Anticipated Serious Adverse Device Effect
ASR	Annual Safety Report
CA	Competent Authority
CEC	Competent Ethics Committee
CIP	Clinical investigation plan
CRF	Case Report Form (pCRF paper CRF; eCRF electronic CRF)
DD	Device Deficiency
DMC / DSMC	Data Monitoring Committee, Data Safety Monitoring Committee
IB	Investigator's Brochure
HSB	Hemanext Storage Bag
ICF	Informed Consent Form
ICH-GCP	International Council for Harmonisation – guidelines of Good Clinical Practice
IFU	Instruction For Use
ISF	Investigator Site File
ISO	International Organisation for Standardisation
MD	Medical Device
MDR	Medical Device Regulation (EU) 2017/745 of 5 April 2017
ORB	Oxygen Reduction Bag
PI	Principal Investigator
SADE	Serious Adverse Device Effect
SAE	Serious Adverse Event
SDV	Source Data Verification
SOP	Standard Operating Procedure
USADE	Unanticipated Serious Adverse Device Effect

SUMMARY OF THE REVISION HISTORY IN CASE OF AMENDMENTS

Version Nr, Version Date	Chapter	Description of change	Reason for the change
A00 11 January 2022	All	Initial release	Initial release
AA 28 April 2022	All	Based on REK letter dated March 07 th , 2022	Amendment 1

3.4 Laboratory

Not applicable. Only standard of care laboratory assessments will be performed.

3.5 Monitoring institution

Monitoring will be performed by the Sponsor or designee.

3.6 Data Monitoring Committee

A Data Monitoring Committee (DMC) will be formed to ensure the safety of the patients participating in the investigation.

This group will provide review and adjudication of all adverse events collected during the clinical investigation. The DMC members will be selected in collaboration between the principal investigator and Hemanext before initiation of the trial.

All DMC members are free from any direct involvement with the trial. Any competing interests, both real and potential, must be declared.

A report outlining the review of adverse events will be included in the Final Study Report.

A DMC charter will be established to document the following but not limited to:

- a) the responsibilities and scope of activities of the DMC;
- b) the frequency, format, and documentation of meetings;
- c) arrangements for handling emergency situations.

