	A first cohort of 5 patients – solely from the hematological malignancies (chronically transfused) group - will be enrolled, transfused and followed-up until their subsequent transfusion or 28 days (+/- 1 day) post-transfusion, whichever comes first
	All safety related data from this initial cohort of 5 patients will be reviewed and assessed by the clinical investigation Data Monitoring Committee (DMC).
	•
	Upon favourable opinion from the clinical investigation DMC, the enrolment of the remaining patients (both groups) will resume until completion.
	Day 0 Planned Transfusion Episode Day 7 Day 28*
	Pt. Screening Enrollment Day 1 (+/- 1 day) (+/- 1 day)
	Visit 0 (V0) Visit 1 (V1) Visit 2 (V2) Visit 3 (V3) Visit (V4) Last Visit (V5)
	Pt. Information Pt. consent Transfusion Phone call On site visit
	BURN – 2 units Hemanext / xx standard units
	HEMATOLOGY – 2+ units Hemanext
	NB: * Day 28+/- 1 day or next transfusion episode, whichever happens first.
Inclusion / exclusion criteria:	INCLUSION CRITERIA
	Patients meeting the following criteria may be invited to participate in the clinical investigation and

	undergo the informed consent process:					
	 A. Hematological malignancies patients group: Male or female patients at least 18 years of age Patients expected to require ≥ 2 units of red blood cells in a single transfusion event Patients who have the capacity to consent to particpate and are willing to comply with the study procedures. Patients identified by a Transfusion hemoglobin trigger of less than 9 g/dL Patients with a documented diagnosis of leukemia, myelomatosis or MDS requiring chronic transfusions 					
	 B. Burn patients group: Male or female patients at least 18 years of age Patients who have the capacity to consent by themselves to participate to the clinical investigation Smaller burn patients, hospitalized with a Total Body Surface Area (TBSA%) burn ≥ 10% and ≤ 50% Patients expected to require ≥ 2 unit of red blood cells in a single transfusion event 					
	EXCLUSION CRITERIA					
	Patients meeting any of the exclusion criteria may not participate in the clinical investigation.					
	A. Both patients groups					

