	 Transfusion of two units of Red Blood Cells, Leukocytes reduced, O₂/CO₂ reduced (single transfusion course) manufactured with the Hemanext ONE System, combined with PRN standard Red Blood Cells, as applicable. Patient's diary
Control intervention (if applicable):	Not applicable
Number of subjects with rationale:	10 acute burn patients and 10 patients with haematological malignancies, who require transfusion of red cells concentrates and who fulfil all eligibility criteria will be enrolled in this clinical investigation at Haukeland University Hospital.
	A total of twenty patients will be sufficient to assess preliminary safety of O ₂ /CO ₂ reduced RBCs, as the standard rate of transfusion related adverse events is usually low and these expected events are well known. If any unexpected adverse events (any type or grade) should occur, they will be identified as such.
Duration of the investigation:	This clinical investigation is estimated to last for a period of approximately 6 months.
Investigation	Anticipated Start Date: May – June 2022
schedule:	Anticipated End Date: November – December 2022
Investigator(s):	Principal Investigator: [name]
	Address: Haukeland University Hespital [name]
	Haukeland University Hospital, [name]
	Norway
	Phone:
	E-mail:

	Sub-Investigator: [name] Address : Haukeland University Hospital, [name] Norway E-mail:
Investigational Site(s):	This clinical investigation will only involve one single clinical site:
	Haukeland University Hospital [name] Norway
Blood Bank	Oslo: Address: Department of Immunology and Transfusion Medicine Section for Blood processing Oslo University Hospital Ullevål Norway
	Bergen: Address:
	Address: Haukeland University Hospital Department of Immunology and Transfusion Medicine [name] Norway E-mail:
Data Monitoring Committee (DMC)	Membership: Professor of intensive care medicine

	Haukeland University Hospital, Bergen
	Chief of Burns, Plastic and reconstructive surgeon
	Haukeland University Hospital, Bergen
	Pland Pank, Haukaland University Heanital, Person
	Blood Bank - Haukeland University Hospital, Bergen
	Blood Bank - Haukeland University Hospital, Bergen
	Blood Bank - Haukeland University Hospital, Bergen
Statistical considerations:	This clinical investigation is not statistically powered – only descriptive statistical methods will be applied

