10.1.1 Experimental Intervention (medical device)

Units of hypoxic RBCs will be manufactured at Oslo's University Blood Bank or Haukeland University Hospital's Blood Bank using Hemanext ONE system. The hypoxic RBCs manufactured in Oslo will be shipped to the Blood Bank at Haukeland University Hospital where they will be stored at 1-6°C for up to 42 days. Participants who would normally receive a transfusion of units of conventional RBCs will instead receive a transfusion of 2 units of hypoxic RBCs and any additional conventional RBCs as needed. All transfusions will be performed according to the site's SOPs.

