12. SAFETY

12.1 Definition and Assessment of (Serious) Adverse Events and other safety related events

Adverse Event (AE) (Art. 2 Abs 57 MDR)

Any untoward medical occurrence, unintended disease or injury or any untoward clinical signs (including an abnormal laboratory finding) in subjects, users or other persons whether or not related to the medical device.

Serious Adverse Event (SAE) (Art. 2 Abs 58 MDR)

Any adverse event that led to any of the following:

- (a) death,
- (b) serious deterioration in the health of the subject that resulted in any of the following:
 - (i) life-threatening illness or injury,
 - (ii) permanent impairment of a body structure or a body function,
 - (iii) hospitalisation or prolongation of patient hospitalisation,
 - (iv) medical or surgical intervention to prevent life-threatening illness or injury or permanent impairment to a body structure or a body function,
 - (v) chronic disease,
- (c) foetal distress, foetal death or a congenital physical or mental impairment or birth defect.

Note: planned hospitalization for pre-existing condition, or a procedure required by the CIP, without a serious deterioration of the health status of the subject, is not considered an SAE

Device deficiency (Art. 2 Abs 59 MDR)

Inadequacy of a medical device related to its identity, quality, durability, reliability, safety or performance, of an investigational device, including malfunction, user errors and inadequate information supplied by the manufacturer. Device deficiency data will be collected by the blood banks and the clinic staff.

The blood bank teams will use the Hemanext ONE System to manufacture hypoxic RBCs. The Oslo blood bank will ship the hypoxic RBCs to the Bergen blood bank team for storage. Bergen blood bank team will confirm blood bag integrity prior to storage, when ordered for a subject and after each transfusion.

Malfunction (ISO14155)

Failure of an investigational device to perform in accordance with its intended purpose when used in accordance with the instructions for use or the CIP.

Device deficiency with Serious Adverse Device Effect (SADE) potential (Art. 80 Abs 1 letter c MDR; ISO14155)

Any device deficiency that might have led to a serious adverse event if appropriate action had not been taken, intervention had not occurred, or circumstances had been less fortunate.

Adverse Device Effect (ADE) (ISO14155)

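### The protocol says DMC members have no direct involvement in the trial, yet a listed affiliation is a blood bank that helps make, store and check the study product

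*Protocol*

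**What the plan says.** Protocol section 3.6 sets out the committee's task: "This group will provide review and adjudication of all adverse events collected during the clinical investigation". On independence it states: "All DMC members are free from any direct involvement with the trial". It requires real and potential competing interests to be declared, asks for a charter, and places a report of the adverse-event review in the Final Study Report. On appointment it says: "The DMC members will be selected in collaboration between the principal investigator and Hemanext before initiation of the trial".

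The synopsis adds a decision role. After a first cohort of 5 haematology patients: "Upon favourable opinion from the clinical investigation DMC, the enrolment of the remaining patients (both groups) will resume until completion". SAP section 4 repeats this step and says nothing about membership.

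The synopsis gives the membership by role or department, all at Haukeland University Hospital, the only clinical site: a professor of intensive care medicine, "Chief of Burns, Plastic and reconstructive surgeon", and "Blood Bank - Haukeland University Hospital, Bergen". The blood-bank line appears more than once and names are removed, so the number of members from that department cannot be told.

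The same department has work to do in the trial. Section 10.1.1 says: "Units of hypoxic RBCs will be manufactured at Oslo's University Blood Bank or Haukeland University Hospital's Blood Bank using Hemanext ONE system". Section 12.1 says: "Bergen blood bank team will confirm blood bag integrity prior to storage, when ordered for a subject and after each transfusion".

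**The concern.** The independence sentence and the membership list do not fit together. A department that may process the product, holds it in storage and inspects the bags takes part in the trial by any ordinary meaning of the words.

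What is at stake is the credibility of the committee's judgement on events that could originate in the blood bank. Section 5.8.1.1 names leaks, loss of sterility and haemolysis among the known processing and storage risks. Section 12.9 adds missed or false-negative sickle-trait testing, an undetected leak in the storage bag, and a non-indicated additive solution. These are failures of testing, processing or inspection. A member from the department responsible for those steps would have an interest in how such an event is attributed.

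The design offers little to offset this. The study has one arm and no blinding, section 8.2.3 treats other bias-reducing methods as not applicable, and section 13.3 sets no statistical criteria for termination. The opinion after 5 patients therefore rests on judgement.

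**Working it through.** No arithmetic applies. The check compares the independence statement with the membership list and the duties assigned elsewhere in the protocol.

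1. **Claim.** Section 3.6: every member is free of direct involvement.
2. **Membership.** Synopsis, DMC entry: the Haukeland blood bank in Bergen is a listed affiliation.
3. **Duties of that department.**
   - Manufacture: one of two sites that process the hypoxic units (sections 3.7 and 10.1.1).
   - Storage: units made in Oslo are shipped to Haukeland and stored there (section 10.1.1).
   - Inspection: bag integrity is confirmed at three points, namely before storage, on ordering and after each transfusion (section 12.1).
   - Device deficiencies: collected by the blood banks together with clinic staff (section 12.1).
   - Accountability: the blood banks must account for all devices (section 10.7).
4. **Comparison.** The department in step 2 has all five duties in step 3. Nothing in the documents explains how a member from that department satisfies step 1. The charter topics listed in section 3.6 include no recusal rule, although the list is expressly open-ended.
5. **Where it can matter.** Device deficiency includes user errors (section 12.1), and harm from an error in use is one criterion for a causal relationship (section 12.8.1). A processing or inspection error would thus be both a blood-bank matter and evidence of device-relatedness. The outputs exposed are the go/no-go opinion, the adjudication of relatedness, and the DMC's report.
6. **Where it does not matter.** The primary outcome in section 7.1 is the number of participants with an adverse event of any type or grade, and section 12.1 defines an adverse event whether or not it is related to the device. Moving an event from device-related to unrelated leaves that number unchanged.
7. **The burn member.** The synopsis identifies the head of burns at the only site. Section 9.2.2 says that investigators recruit from the site's burn patients. It does not say who operates or that this member treats anyone in the trial. The first cohort is entirely haematology, so any conflict here would not reach the data behind the go/no-go opinion.

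**The case against.** The strongest reply is that section 3.6 speaks of members, while the synopsis gives only affiliations. A physician in the blood bank may have no hand in making, storing or checking trial units. That stands: the documents show departmental involvement, and no passage shows that a listed individual handles units. It does not settle the matter, because such a member could still be judging work done in their own department.

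A second reply is that section 3.6 already requires competing interests to be declared and provides for a charter, which is not among the documents and could contain a recusal rule. This mitigates the problem. A declaration discloses a conflict without removing it, and the protocol does not say what follows from one.

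A third reply is that other safeguards exist, and it is correct. A reader might infer that the DMC is the sole check on causality ratings. The documents do not support that. Investigator and sponsor each rate serious events (section 12.1). An event is reportable if either rates it above not related (section 12.8.2). Uncertain serious events default to possible (section 12.8.1). All adverse events are listed individually (SAP section 7.8.1), and the SAP does not say that DMC adjudication replaces the other ratings in any table.

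Finally, joint selection of members by the investigator and sponsor contradicts nothing in the documents and is not part of this point.

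**Conclusion.** The independence sentence is not supported by the membership the protocol lists, and the two must be reconciled. The point concerns one listed department with five documented duties. It affects the opinion that releases enrolment after 5 patients, the adjudication of product-quality and device-related events across the 20 planned patients, and the committee's report.

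Two stronger readings are tempting and should be resisted. A reader might infer that the primary result is biased, by 1/20 = 5 percentage points per re-attributed event overall or 1/10 = 10 within a group. Those figures express only the granularity of the sample, and re-attribution does not move a count of participants with any event. A reader might also infer that the head of burns is treating trial patients. That is plausible at a single site, but no passage says so, and it remains an inference.

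The conclusion assumes that the synopsis list is the intended membership and that no recusal rule sits in the charter. It also assumes that the DMC's adjudication concerns attribution rather than whether something counts as an adverse event at all. If the DMC can remove events, the primary count would be exposed too, but the documents do not say that it can.

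**What to change.** Amend section 3.6, the synopsis and the DMC charter in one of two ways:

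- give the blood-bank seat to a transfusion-medicine physician from outside the two manufacturing blood banks; or
- keep the member, with written recusal from adjudicating product-quality and device-related events and from the go/no-go opinion.

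In either case, add that the burn member is recused from events in patients whom that member treats or supervises. This rule does no harm if no such patients exist.

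If the membership is left as it is, correct the sentence in section 3.6 so that it describes the actual affiliations, and report those affiliations with the results.

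The cost is one outside reviewer working remotely, or a recusal procedure, for 20 patients. The committee need not grow, and the SAP needs no change.

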3.7 Any other relevant Committee, Person, Organisation, Institution

The hypoxic RBCs will be processed and provided to the clinical site from either of the following locations:

Department of Immunology and Transfusion Medicine	Department of Immunology and Transfusion Medicine
Oslo University Hospital Ullevål	Haukeland University Hospital
Oslo, Norway	Bergen, Norway

4. ETHICAL AND REGULATORY ASPECTS

The final positive decision of the CEC on the conduct of the investigation will be made and given in writing to the Sponsor before the investigation can begin. Additional requirements set by the CEC must be implemented.

4.1 Registration of the investigation

Registration status:

Hemanext Inc. will comply with the Research Council of Norway on requirements and guidelines for registration and disclosure of medical and health-related studies involving human participants, through: www.ISRCTN.org

4.2 Competent Ethics Committee (CEC)

The Sponsor or designee will submit the investigation to the CEC and obtain ethical committee approval before the start of the investigation. The PI ensures that approval from the CEC is obtained and filed in the Investigator site file before the investigation starts.

4.2.1 Reporting duties to the Competent Ethics Committee

CIP Amendments will be reported according to the applicable requirements and timeframes.

The regular or premature end of the investigation as well as the interruption of the investigation must be reported to the CEC within 15 days (within 24 hours if it is due to security reasons). The reasons for a premature end or an interruption must be explained.

A final report will be submitted within one year after the regular end of the investigation and within 3 months after a premature end of the investigation.

4.3 Competent Authorities (CA)

Notification of this clinical investigation and of the use of hypoxic blood will be made prior the start of this clinical investigation.

4.3.1 Reporting duties to the competent authorities

Notification of this clinical investigation and of the use of hypoxic blood will be made prior the start of this clinical investigation.

4.4 Ethical Conduct of the Investigation

The investigation will be carried out according to the CIP and with principles enunciated in the current version of the Declaration of Helsinki, the European Regulation on medical devices 2017/745 (MDR), the Norms ISO14155 and ISO14971, the ICH-guidelines of Good Clinical Practice (GCP) as applicable, and local regulatory authority's requirements. The CEC, if applicable, will receive the Annual Safety Report (ASR) and interim reports and be notified about investigation stop/end in agreement with local requirements.

4.5 Declaration of interests

Investigators and sub-investigators will provide the sponsor with sufficient, accurate financial information as requested to allow the sponsor to submit complete and accurate financial certification or disclosure statements to the appropriate regulatory authorities. Investigators are responsible for providing information on financial interests during the study and for 1 year after completion of the study.

4.6 Patient Information and Informed Consent

All potential subjects are given a Patient Information Sheet and an Informed Consent Form describing the investigation and providing sufficient information for the subject to make an informed decision about his/her participation in the investigation. The Patient Information Sheet must be provided prior to the Screening Visit. The PI must explain to each subject the nature of the investigation, its purpose, the procedures involved, the expected duration, the potential risks and benefits and any discomfort it may entail. Each subject must be informed that the participation in the investigation is voluntary and that he/she may withdraw from the investigation at any time and that withdrawal of consent will not affect his/her subsequent medical assistance and treatment. The subject should be informed that he/she can ask any question, and consult with family members, friends, their treating physicians or other experts before deciding about their participation in the investigation. Enough time must begiven to the subjects prior to providing informed consent.

The formal consent of a subject, using the approved consent form, is obtained before the subject is submitted to any investigation procedure. The subject should read, understand, and voluntarily agree before signing and dating the informed consent form. The consent form is signed and dated by the subject and the PI (or her/his designee). The subject must be given a copy of the signed document. The original signed and dated consent form is retained as part of the investigation records.

The subjects must be informed that authorised individuals other than their treating physician may examine his/her medical records.

4.7 Subject privacy and confidentiality

The Sponsor and the PI affirm and uphold the principle of the subjects' right to privacy and that they shall comply with applicable privacy laws. Especially, anonymity of the subjects shall be guaranteed when presenting the data at scientific meetings or publishing them in scientific journals.

Individual subject medical information obtained because of this investigation is considered confidential and disclosure to third parties is prohibited.

For data verification purposes, authorised representatives of the Sponsor or the CEC may require direct access to parts of the medical records relevant to the investigation, including subjects' medical history.

To protect the rights and freedoms of participants about the processing of personal data, participants will be assigned a single, participant specific numerical code. Any participant records or data sets that are transferred to the sponsor will contain the numerical code only; participant names will not be transferred. All other identifiable data transferred to the sponsor will be identified by this single, participant specific code. The study site will maintain a confidential list of participants who participated in the study, linking each participant's numerical code to his or her actual identity and medical record identification. In case of data transfer, the sponsor will protect the confidentiality of participants' personal data consistent with the clinical study agreement and applicable privacy laws.

